3.0 Patient Selection

3.1 Inclusion Criteria

- 3.1.1 Cancer patients at Wake Forest Baptist Comprehensive Cancer Center and its satellites who have next generation DNA sequencing results on their tumor biopsy or surgically resected tissue and/or blood samples and/or consent to the WFCCC Precision Oncology Registry to use their information for research.
- 3.1.2 Actionable mutation (defined as a mutation or gene amplification for which an off-label therapy is identified on the patient's NGS report for which NCCN guidelines do not recommend a specific treatment in the particular disease or for which there is no documentation in the patient's medical record of clinical data demonstrating lack of activity with the targeting of the specific mutation or amplification in the patient's specific disease) uncovered by the genomic sequencing of a tumor or those that have undergone liquid biopsy assay of their tumor genomic, performed by Wake Forest or another and who are medically able to receive targeted therapy based on those results.
- 3.1.3 Sequencing on a sample collected within 3 months prior to registration is strongly encouraged but must have been performed within the 12 months prior to registration.
- 3.1.4 Patients must have progressed through at least two lines of treatment, or are not candidates for or unwilling to receive any standard therapies. Patients who have received treatment on the present protocol who have progression of disease may be recruited to the trial for treatment using another targeted therapy provided that they fullfil the other criteria for participation in the trial. If a patient discontinues treatment on this protocol they can be considered for further participation in this trial provided they meet all of the eligibility criteria and are eligible for re-registration and re-consent.
- 3.1.5 ECOG of ≤ 3
- 3.1.6 Life expectancy of greater than 6 weeks

ClinicalTrials.gov: NCT04111107

3.1.7 The effects of the drugs used for cancer treatment on the developing human fetus are unknown. For this reason and because of the possibility that the agents are teratogenic, women of child-bearing potential and men must agree to use adequate contraception (hormonal or barrier method of birth control; abstinence) prior to study entry and for the duration of study participation. Should a woman become pregnant or suspect she is pregnant while participating in this study, she should inform her treating physician immediately.

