3.2 Exclusion Criteria

- 3.2.1 Patients who have had or will receive chemotherapy or radiotherapy to major bone marrow bearing sites within 2 weeks prior to receiving treatment on the study.
- 3.2.2 Patients who have not recovered from toxicity of prior treatment if such toxicity will preclude treatment with the proposed targeted agent.
- 3.2.3 Patients may not be receiving any other investigational agents.
- 3.2.4 Uncontrolled intercurrent illness including, but not limited to ongoing or active infection, symptomatic congestive heart failure, unstable angina pectoris, cardiac arrhythmia, or psychiatric illness/social situations that would limit compliance with study requirements.
- 3.2.5 Pregnant women are excluded from this study because of the potential for teratogenic or abortifacient effects. Because there is an unknown but potential risk for adverse events in nursing infants secondary to treatment of the mother with the targeted agent, breastfeeding should be discontinued if the mother is treated with the targeted agent.

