5.3 Planned EHR Data Collection

The following data points will be collected. The NGS data will consist of the clinical NGS data report, sequence variant reports (example: VCF or variant call files), binary DNA sequence alignment data (BAM files or SAM files), and any quality control reports supporting the validity of the clinical NGS data. The accompanying clinical data will be extracted from the clinical records (through manual and automated processes) and will include demographic information, diagnoses, and medical treatments in addition to information regarding the relationship of NGS to treatment decisions.

- Age, gender, ethnicity, race, insurance type and coverage
- Marital status
- Occupation
- Educational level
- Military service
- Family medical history
- Patient's medical history
 - Previous cancer diagnoses and treatments
 - Previous or current conditions
 - Current prescription medications
- Treating physician and physician ordering tumor DNA sequencing
- Extent of financial assistance provided if applicable
- Vendor used for tumor DNA sequencing

ClinicalTrials.gov: NCT04111107

- Previous and current tobacco and alcohol use information if available
- The date of DNA sequencing results and date of results discussion
- If NGS data revealed somatic mutations warranting further investigation by Genetic Counseling, the type of mutation present and the referral date to Genetic Counseling
- Type of treatment plan toward mutation of interest if applicable/known
- Response and progression-free survival for last known treatment
- Progression-free and overall survival times for new targeted therapy
- Response to new targeted therapy

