	Pre-Study ^a	Cycle 2, Day 1	Day 1; every even cycle (after cycle 2)	End of Treatment ±7 days	Follow up for Safety (30+ days after last treatment) required only if pt has treatment related AEs at end of treatment visit
Informed Consent	X				
Demographics	X				
Medical History	X				
Concurrent Meds	X				
Physical Exam	X	X	X	X	X
Vital Signs	X	X	X	X	X
Performance Status	X	X	X	X	X
Bone Marrow Biopsy ^h	X	X	X	X	
Imaging ^d	X	X	X ^f	X	
CBC w/diff, platelets ^e	X	X	X	X	X
Serum Chemistry ^b	X	X	X	X	X
B-HCG ^c	X				
Dose Adjustment Form		X	X		
Adverse Event Evaluation		X	X	X	X
Survival Status/Telephone Follow up ^g					X
PROMIS 29	X	X		X	
Satisfaction with Medical Decision Scale	X	X		X	
Patient Reported Outcome- Demographics/Health Literacy	X				

^a Pre-study requirements listed in table must be completed **within** 30 days prior to registration. Imaging demonstrating disease progression should be completed within 60 days of registration. Imaging should be repeated if the scan occurred more than 30 days prior to treatment initiation..

^b Albumin, alkaline phosphatase, total bilirubin, bicarbonate, BUN, calcium, chloride, creatinine, glucose, potassium, total protein, SGOT[AST], SGPT[ALT], sodium.

^c Serum pregnancy test within 10 days of Pre-study visit (women of childbearing potential only).

^d Imaging will be performed as part of SOC for solid tumors every other cycle, however due to patients on different drug treatment regimen, this may occur at 6 weeks ±2 weeks, 8 weeks ± 2 weeks or 12 weeks ± 2 weeks. Not required for leukemias. As clinically indicated in Multiple myeloma.

^e Labs will be performed in accordance with the recommendations of the prescribing instructions for the drug that is utilized

^f If treatment is discontinued for reasons other than progression, imaging will be performed on the same schedule as was utilized while patient was receiving treatment until progression.

^g Survival and information related to cancer treatment received after the study and disease status is monitored bimonthly via telephone contact or EMR review after treatment termination. Medical record review will be performed to coincide with the bimonthly telephone call to obtain information regarding evidence and of relapse (as documented on CT, PET, biopsy, etc).

^h If clinically indicated bone marrow biopsy will be repeated to evaluate response to therapy.

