8.1.1 Definitions

- **Evaluable for toxicity:**

All patients will be evaluable for toxicity from the time of their first treatment with the study treatment of interest.

- **Evaluable for objective response:**

Only those patients who have measurable disease present at baseline, have received at least one cycle of therapy, and have had their disease re-evaluated will be considered evaluable for response. These patients will have their response classified according to the definitions stated below. (Note: Patients who exhibit objective disease progression prior to the end of cycle 1 will also be considered evaluable.)

- **Evaluable Non-Target Disease Response.**

Patients who have lesions present at baseline that are evaluable but do not meet the definitions of measurable disease, have received at least one cycle of therapy, and have had their disease re-evaluated will be considered evaluable for non-target disease. The response assessment is based on the presence, absence, or unequivocal progression of the lesions.

- **Measurable disease / measurable lesions**

Measurable lesions are defined as those that can be accurately measured in at least one dimension (longest diameter to be recorded) as ≥ 20 mm by chest x-ray, as ≥ 10 mm with CT scan, or ≥ 10 mm with calipers by clinical exam. All tumor measurements must be recorded in millimeters (or decimal fractions of centimeters).

- **Malignant lymph nodes.**

To be considered pathologically enlarged and measurable, a lymph node must be ≥ 15 mm in short axis when assessed by CT scan (CT scan slice thickness recommended to be no greater than 5 mm). At baseline and in follow-up, only the short axis will be measured and followed.

- **Non-measurable disease / non-measurable lesions:**

All other lesions (or sites of disease), including small lesions (longest diameter <10 mm or pathological lymph nodes with ≥ 10 to <15 mm short axis), are considered non-measurable disease. Bone lesions, leptomeningeal disease, ascites, pleural/pericardial effusions, lymphangitis cutis/pulmonitis, inflammatory breast disease, and abdominal masses (not followed by CT or MRI), are considered as non-measurable.

Note: Cystic lesions that meet the criteria for radiographically defined simple cysts should not be considered as malignant lesions (neither measurable nor non-measurable) since they are, by definition, simple cysts.

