14.3 Analysis of Secondary and Exploratory Objectives

Response rate will be estimated for all patients with corresponding 95% confidence intervals. Progression-free survival and overall survival times will be displayed using Kaplan-Meier curves with median survival times and confidence intervals. Adverse events will be summarized in incidence tables by type and grade severity for all patients and presented by type of treatment received. For exploratory objectives, the frequency of types of actionable mutations and previous treatment history will be summarized and demographic characteristics presented. Logistic models will be constructed for each type of mutation (yes/no) to preliminarily explore associations with clinical and demographic characteristics. For quality of life and patient satisfaction outcomes, changes over time will be assessed using a repeated measures ANOVA, with any between time associations utilizing Tukey adjustment for post-hoc comparisons. Transformations and/or non-parametric approaches will be considered for any outcomes violating parametric assumptions.

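### Nothing in the plan keeps pre-existing symptomatic toxicity out of the per-agent adverse event tables: symptoms have no required baseline grade and there is no new-or-worsened rule

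*Combined protocol and SAP*

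**What the plan says.** **Entry.** Section 3.2.2 excludes "Patients who have not recovered from toxicity of prior treatment if such toxicity will preclude treatment with the proposed targeted agent". Other unresolved toxicity is no bar to entry. The washout in 3.2.1 covers chemotherapy, or radiotherapy to marrow-bearing sites, "within 2 weeks prior to receiving treatment on the study". Section 3.1.4 also allows re-entry for a different drug (sentence cut short here): "Patients who have received treatment on the present protocol who have progression of disease may be recruited to the trial for treatment using another targeted". ECOG status up to 3 is accepted (3.1.5).

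**Collection.** In the schedule in section 6.0, the row "Adverse Event Evaluation" is blank at Pre-Study and marked at Cycle 2 Day 1, at later even cycles, at end of treatment and at safety follow-up. Footnote a begins "Pre-study requirements listed in table must be completed" and sets a window of 30 days before registration. The items marked at Pre-Study include medical history, concurrent medications, physical exam, performance status, blood count and chemistry. Section 5.3 adds "Previous or current conditions" from the health record, with no mention of a grade. Section 9.1 adopts CTCAE v5.0 and a five-level attribution scale.

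**Analysis.** Section 8.1.1 states: "All patients will be evaluable for toxicity from the time of their first treatment with the study treatment of interest". Section 5.2.2 sets as a secondary outcome the incidence of adverse events, serious adverse events and laboratory abnormalities for each agent. Section 14.3 says "Adverse events will be summarized in incidence tables by type and grade severity for all patients", and that they are also presented by treatment received.

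**The concern.** Safety is a secondary objective (2.2.3) and the trial has a single arm (14.2). No control group shows how common fatigue, pain or neuropathy would be in these patients without the study drug. A pre-treatment grade is the usual way to separate what was already there from what appeared or worsened on treatment.

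The schedule asks for no such grade for symptoms, and the analysis text does not say that only new or worsened events count. A symptom left over from earlier therapy and first graded at Cycle 2 Day 1 could therefore stand in the table as an event on the study drug.

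Any distortion could also differ between agents. Exclusion under 3.2.2 depends on which drug is proposed, and step 7 of the algorithm in 6.0 moves a patient with a label contraindication to the next listed drug. Residual toxicity can thus influence which agent a patient receives, and so whose row in the table carries it.

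**Working it through.** The plan states no figure on this point, so there is none to reproduce. The check is a cross-reading, followed by an illustration under assumed rates.

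**Cross-reading**

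1. *Can pre-existing toxicity enter?* Yes, if it does not preclude the proposed agent (3.2.2). On re-registration it may come from an earlier study drug (3.1.4).
2. *Is it graded before treatment?* The adverse event row has four marks for five columns, and the empty cell is Pre-Study. Neighbouring rows such as physical exam and blood count do carry a Pre-Study mark. Blood count and chemistry values allow laboratory abnormalities to be graded at baseline. For symptoms, no CTCAE grade is required.
3. *Does the analysis remove it?* Section 8.1.1 starts the count at first treatment but sets no condition that an event be new or worse. Section 14.3 names neither baseline nor attribution. No definition of a treatment-emergent event appears in the documents.

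**Illustration (all rates assumed; the documents give none)**

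Let c be the share of patients who enter with a given symptom that persists and is logged as an event, p the share of the others who newly develop it, and w the share of those with the symptom at baseline in whom it worsens.

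- Tabulated incidence = c + (1 − c)p
- Incidence of new or worsened events = (1 − c)p + cw
- Excess = c(1 − w)

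With p = 10%:

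| c | Tabulated | New or worsened, w = 0 | New or worsened, w = 10% |
|---|---|---|---|
| 5% | 5 + 9.5 = 14.5% | 9.5% | 9.5 + 0.5 = 10% |
| 10% | 10 + 9 = 19% | 9% | 9 + 1 = 10% |
| 20% | 20 + 8 = 28% | 8% | 8 + 2 = 10% |
| 30% | 30 + 7 = 37% | 7% | 7 + 3 = 10% |

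The excess is 5 to 30 percentage points if no baseline symptom worsens, and 4.5 to 27 points if 10% do. It falls to zero if all of them worsen, or if staff log none of the unchanged symptoms. With p = 30% and the same values of c, the tabulated incidence is 33.5%, 37%, 44% and 51%.

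**The case against.** The strongest reply is that the plan never says carried-over toxicity is to be counted. Sections 8.1.1 and 9.2 speak of the period from first treatment and of events during the intervention, and staff may reasonably not log an unchanged condition as an event. This stands: a reader might infer that such toxicity is certain to be in the tables, and the documents do not support that. They give no rule either way. What can be said is that nothing keeps it out, and that practice may vary between staff.

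A reader might also infer that a baseline grade is the only means of separation, or that baseline status is lost for good. Neither is supported. Attribution is recorded on five levels (9.1), and the schedule relies on it when it ties the safety follow-up visit to treatment-related events. Pre-study laboratory values can be graded. The fields of the medical history form are not in the documents, and clinical records can be searched. These are partial safeguards: 14.3 uses none of them, attribution is harder to judge without a baseline grade, and symptom grades rebuilt from records are less reliable than grades taken at the visit.

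Entry is also limited by label requirements for organ and marrow function, by contraindications, and by the exclusion of uncontrolled illness. Carry-over is therefore plausibly mostly of lower grade, and tabulation by grade would confine much of it to the lower-grade rows. Not every patient has had two prior lines, since 3.1.4 also admits those who cannot or will not have standard therapy.

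Finally, the safety objective is descriptive, 14.1 says that particular treatments are not the target, and no threshold hangs on these tables. That limits the weight of the point but does not remove it, because 5.2.2 still asks for incidence per agent.

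**Conclusion.** The concern holds as a gap in collection and analysis. Unresolved prior toxicity may enter, symptoms have no required CTCAE grade before treatment, and 14.3 has no rule that would keep unchanged pre-existing symptoms out of the incidence by treatment received. Laboratory abnormalities are less affected because pre-study values exist, and attribution is a partial safeguard.

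The likely bias is upward, but its size cannot be given from the documents. The range of 14.5% to 37% against an assumed 10% new onset rests on assumed carry-over of 5% to 30%, on persistence of the symptom, and on its being logged. Some of that excess would be legitimate where baseline symptoms worsen.

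The tables are by treatment received, which need not be the drug first selected, so the point concerns the drug actually given. The primary analysis and the serious adverse event reporting to the DSMC do not depend on it. It is a cheap improvement to a secondary outcome.

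**What to change.** - **Schedule (6.0):** mark the adverse event row at Pre-Study and record there the CTCAE v5.0 grade of each ongoing symptom and toxicity. Do this again at each re-registration, so that toxicity from an earlier study drug is on record before the next one starts.
- **Section 14.3:** define the tabulated events as those that are new, or worsened in grade, from that baseline. Present them by treatment received, with attribution alongside.
- **Laboratory abnormalities:** report shift in grade from the pre-study values already collected.

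No entry rule or treatment rule needs to change. The cost is a few minutes of extra data entry per patient at a visit that already takes place, plus a few sentences in the analysis section.

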4.0 Registration Procedures

All patients entered on any WFBCCC trial, whether treatment, companion, or cancer control trial, **must** be linked to the study in EPIC within 24 hours of Informed Consent. Patients **must** be registered prior to the initiation of treatment.

You must perform the following steps in order to ensure prompt registration of your patient:

1. Complete the Eligibility Checklist (Appendix A)
2. Complete the Protocol Registration Form (Appendix B)
3. Alert the Cancer Center registrar by phone, *and then* send the signed Informed Consent Form,
4. Eligibility Checklist and Protocol Registration Form to the registrar, either by fax or e-mail.

Contact Information:

Protocol Registrar [contact]

Protocol Registrar [contact]

Protocol Registrar E-MAIL ([contact])

*Protocol Registration is open from 8:30 AM - 4:00 PM, Monday-Friday.

5. Fax/e-mail ALL eligibility source documents with registration. Patients **will not** be registered without all required supporting documents.

Note: If labs were performed at an outside institution, provide a printout of the results. Ensure that the most recent lab values are sent.

To complete the registration process, the Registrar will:

- assign a patient study number
- assign the patient a drug and dose
- register the patient on the study

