- 7) Once an actionable mutation is selected, if more than one drug is listed as a possible treatment, the drug(s) corresponding to the patient's Treatment Number listed in the tumor analysis report for the selected mutation will be selected as treatment. Patients must have adequate organ and marrow function to permit administration of the study drug as specified in the drug packaging label. If the subject has a medical contraindication to the selected drug (according to the drug label) or the selected drug(s) cannot be obtained for the patient, the study team will select the next drug(s) presented by the tumor sequencing report. If necessary, this process will be repeated until a suitable drug is selected, returning to the top of the list of the drugs listed for the selected mutation if necessary. If the list of drugs proposed for the selected actionable mutation is exhausted, then the next listed actionable mutation will be selected and the process repeated, if necessary returning to the top of the list of actionable mutations if the first selected mutation is not at the top of the list on the report. Documentation for why particular drugs were not selected, if applicable, will be obtained for alternative

[figure not shown]
Patient has NGS performed as prescribed by their doctor and/or is entered in the Precision Medicine RegistryCCCWFU 04218 IPR00054757

and has failed at least **Is the Mutational Frequency listed on the NGS Report?** receive standard therapy

Precision medicine for patients with identified actionable mutations at Wake Forest Baptist
Comprehensive Cancer Center (WFBCCC): A pragmatic trial
WFBCCC # 04519

ClinicalTrials.gov: NCT04111107

therapies in order to evaluate some of the potential barriers to treatment using the NGS method.

If NGS report lists the mutational frequency, targeted mutation will be the highest frequency mutation

Precision medicine for patients with identified actionable mutations at Wake Forest Baptist Comprehensive Cancer Center (WFBCCC): A pragmatic trial
WFBCCC # 04519

If no mutational frequency listed on NGS report, the actionable mutations will be assigned, in the manner below (based on their presentation in the NGS report):

If single actionable mutation is identified	2-5 actionable mutations	6-10 actionable mutations	11-15 actionable mutations	>-15 actionable mutations

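### The one scheduled pregnancy test is timed from the Pre-study visit and registration, not from first dose, so a compliant test can be 30 days old plus any delay to treatment.

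*Combined protocol and SAP*

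**What the plan says.** The B-HCG row of the study-activities table (section 6.0) has a single mark, in the Pre-Study column. Footnote c gives its timing: "Serum pregnancy test within 10 days of Pre-study visit (women of childbearing potential only". It does not say whether the 10 days run before or after the visit, and it does not mention treatment.

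Footnote a governs the whole Pre-Study column: "Pre-study requirements listed in table must be completed" within 30 days before registration. For imaging only, it adds a rule tied to the start of therapy: "Imaging should be repeated if the scan occurred more than 30 days prior to treatment initiation".

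Section 4.0 fixes the order of events, since patients must "be registered prior to the initiation of treatment", but gives no longest interval. At registration the registrar is to "assign the patient a drug and dose". Step 7 of the treatment algorithm moves to the next listed drug if "the subject has a medical contraindication to the selected drug (according to the drug label) or the selected drug(s) cannot be obtained", and repeats this as needed with no time limit.

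The test supports exclusion 3.2.5: "Pregnant women are excluded from this study because of the potential for teratogenic or abortifacient effects". That criterion names no test and no date.

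**The concern.** A pregnancy test protects a patient only if it is recent when exposure begins. Here the test's age is limited at registration, while exposure begins at first dose, and nothing limits the time between the two. Where the assigned drug's label does not call for a test, a site could follow the schedule exactly and start a possibly teratogenic drug on a result a month or more old. The harm at stake is the one that 3.2.5 names.

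The protocol recognises elsewhere that pre-study information can go stale before dosing. The imaging repeat in footnote a, the lesion-measurement baseline in 8.1.2 and the washout in 3.2.1 all count to the start of treatment. The pregnancy test does not.

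**Working it through.** The plan states no figure for the age of the test at first dose, so there is none to reproduce. The check is interval arithmetic on the stated windows.

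**Inputs**
- Longest time from test to registration: 30 days (footnote a, which covers every item in the Pre-Study column, B-HCG included).
- Time from registration to first dose: g days. Section 4.0 requires only that registration comes first, so g has no stated maximum.
- Later scheduled pregnancy tests: none (one mark in the B-HCG row).

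**Formula**
Maximum age of a compliant test at first dose = 30 + g days.

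| g (days) | Source of g | Maximum age at first dose |
|---|---|---|
| 0 | first dose on the day of registration | 30 + 0 = 30 |
| 7 | assumption | 30 + 7 = 37 |
| 14 | constructed worst case from 3.2.1 | 30 + 14 = 44 |
| 28 | assumption | 30 + 28 = 58 |

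**Where g = 14 comes from.** Exclusion 3.2.1 bars chemotherapy, or radiotherapy to marrow-bearing sites, "within 2 weeks prior to receiving treatment on the study". It counts to treatment, so it does not stop a patient from being registered on the day of her last such therapy and then waiting out the 2 weeks. The 44-day figure needs that and also a test taken at the very edge of the 30-day window.

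**Is a delay plausible?** Yes, though its usual length cannot be read from the documents. The drug is assigned at registration and may then have to be replaced under step 7. Section 1.0 lists access, cost and reimbursement as known obstacles to off-label targeted therapy.

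**Does any other rule set the missing limit?**
- 8.1.2 has a 4-week limit before treatment, but it belongs to the methods for measuring lesions.
- Footnote e refers labs to the drug's prescribing instructions. Its marker is on the CBC row, and it gives no window.
- 6.1.1 and step 7 rely on the label, so they help only where the label calls for a test.
- 3.1.7 requires agreement to contraception and prompt reporting of a suspected pregnancy. Neither is a test.
- Appendix A asks for a documented source, with dates and lab results, for each criterion, and has a treating-physician signature line. It confirms eligibility at registration, not at first dose.

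**After the fix.** With a 10-day window counted back from treatment initiation, the maximum age is 10 days whatever the value of g.

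**The case against.** The strongest reply is that the remaining gap is narrow. Pregnancy is an exclusion, a serum test is already required, and contraception is mandatory. The treating physician doses by the label, has the dated result available through the Appendix A documentation, and is to be told at once of a suspected pregnancy. Footnote e, although marked on the CBC row, is worded generally enough to bring in any test that the label recommends. Section 4.0 refuses registration without source documents and asks for the latest laboratory values. Appendix B asks for the treatment start date on the registration form, which suggests that dosing may often follow registration closely. At g = 0 the maximum of 30 days equals the age that footnote a tolerates for imaging at treatment start.

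Most of this stands as mitigation. It narrows the exposed group to women of childbearing potential whose drug label calls for no test and whose physician does not retest. It does not supply the missing rule: the label provisions vary by drug, the eligibility documents act at registration, and a date field on a form is not a limit.

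A reader might also infer a larger figure, 40 + g days, by placing the visit 30 days before registration and the test 10 days before the visit. The documents do not support that. B-HCG is listed in the Pre-Study column, so footnote a's 30-day requirement applies to the test itself. Footnote c adds a condition and nothing says that it overrides footnote a. A test 40 days before registration would breach the protocol.

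**Conclusion.** The point holds as a cheap safety improvement. The protocol limits the age of its only scheduled pregnancy test at registration (30 days) but not at first dose, where a compliant test can be 30 + g days old with no upper limit. That is 30 days at g = 0 and 44 days at g = 14; the latter is permitted by 3.2.1 but is a constructed extreme, not a typical case.

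The conclusion rests on footnote a binding the B-HCG test and on the absence of any stated limit for g. The documents do not give the usual g, the number of women of childbearing potential, or the share of drugs whose labels call for a test, so the number of patients affected is unknown and may be small. A reader should not infer that patients will commonly be dosed on stale tests, or that the protocol leaves pregnancy unguarded; the documents show neither. Sample size, power and the primary analysis are unaffected.

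**What to change.** Re-anchor footnote c to the start of therapy, for example: *Negative serum pregnancy test within 10 days before treatment initiation (women of childbearing potential only), repeated if the first dose is delayed beyond this window.*

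This keeps the footnote's own 10 days, states that the result must be negative, and removes the doubt about which direction the 10 days run. The length is a clinical choice, and the sponsor may prefer another fixed window; what matters is that it counts back from first dose.

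The cost is one edited footnote and an occasional repeat blood test for a woman whose screening result falls outside the window when dosing begins.
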